Event	Decision	Date of event or censor to consider for analysis
Clinical disease progression or death from any cause	Not censored	Date of clinical disease progression or death
No clinical disease progression and no death and no premature withdrawal from the study	Censored	Date of last visit
No clinical disease progression no death and patient premature withdrawal from the study or lost to follow-up	Censored	Date of withdrawal from the study or last contact

- OS

Event	Decision	Date of event or censor to consider for analysis
Death from any cause	Not censored	Date of death
Patient alive and no premature withdrawal from the study	Censored	Date of last visit
Patient premature withdrawal from the study or lost to follow-up	Censored	Date of withdrawal from the study or last contact

- Disease-specific mortality

Event	Decision	Date of event or censor to consider for analysis
Death related to prostate cancer	Not censored	Date of death
Death not related to prostate cancer	Censored	Date of death
Patient alive and no premature withdrawal from the study	Censored	Date of last visit
Patient premature withdrawal from the study or lost to follow-up	Censored	Date of withdrawal from the study or last contact

- PSADT

Event	Decision	Date of event or censor to consider for analysis
First PSA value > than twice that of the first increased value (> 0.2 ng/mL)	Not censored	Date of sample when the first PSA value > than twice that of the first increased value
No PSA value 2 times higher than the first increased value or no increased value and no premature withdrawal from the study	Censored	Date of last evaluable sample
Patient premature withdrawal from the study or lost to follow-up	Censored	Date of last evaluable sample before withdrawal from the study or last contact

Incomplete dates for time-to-event analyses will be handled as follows:

- If the day of the randomisation is missing and month is present, the 15 of the month will be used.
- If the day of the BR, clinical progression or death is missing and month is present, the 01 of the month will be used.
- If the month (or the date) of the death is missing, the date of the last contact will be used.
- The other dates with missing month will be studied case by case.

Castrated patients

A patient will be considered as:

- Castrated if the testosterone level is inferior to 50 ng/dL for the test or confirmation test.
- Not castrated if the testosterone level is superior or equal to 50 ng/dL for the test and confirmation test.

HRQoL

- FACT-P

The FACT-P score is composed of 27 general questions about physical, social, emotional, and functional well-being as well as a 12-item questionnaire about prostate-specific concerns. A maximum score of 156 points indicates the highest level of QoL. The total FACT-P score will be calculated as the sum of 39 item scores.

Dimensions	Subscales	Number of items	N° item
General well-being	Physical well-being	7	GP1 to GP7
	Social well-being	7	GS1 to GS7
	Emotional well-being	6	GE1 to GE6
	Functional well-being	7	GF1 to GF7
Prostate-specific concerns	--	12	C2, C6 P1 to P8 BL2 to BL5

For missing data, if less than 50 % of the items are missing, subscale scores will be prorated. This will be done by using the formula below:

Prorated subscale score = (Sum of item scores)*(Number of items in the subscale)/
(Number of items answered).

If more than 50 % of the items are missing from any subscale, the subscale will not be imputed.

For any given scale, if the missing values represent more than 10 % of the population; two analyses will be performed. One analysis using the available values and a second analysis imputing the missing values by the mean value of the available data at the concerned timepoint will be performed.

- SF-36v2

The SF-36 health survey version 2 [1] is composed of 36 items about 8 Health Domain Scales: Physical Functioning (PF), Role-Physical (RP), Bodily Pain (BP), Social Functioning (SF), Mental Health (MH), Role-Emotional (RE), Vitality (VT) and General Health (GH).

All but one of the 36 items (item n°2: self-reported health transition) are used to score the eight raw Health Domain Scales. Each item is used in scoring only one scale. The response for each item is recoded according to the table below.

Then, the eight Health Domain Scales Total Raw Scores are calculated, according to the table on the following page. Each score will range from 0 to 100, where 0 represent the lowest possible score (worst health state) and 100 represent the highest possible score (best health state).

Finally, the eight health domain scales scores are normed to the 2009 U.S. general population to have a mean of 50 and a standard deviation of 10. These are health domain scales norm-based scores.

Two summary measures are calculated, using the eight health domain scales norm-based scores and an algorithm: an overall score of physical health (Physical Component Summary or PCS) and overall score of mental health (Mental Component Summary or MCS)

Item numbers	Precoded response value	Final response value
3a to 3j	1 2 3	3 2 1
2 4a to 4d 5a, 5b, 5c 9b, 9c, 9f, 9g, 9i 10, 11a, 11c	1 2 3 4 5	5 4 3 2 1
7	1 2 3 4 5 6	6 5 4 3 2 1
1 6 8 9a, ,9d, 9e, 9h 11b, 11d	1 2 3 4 5	5 4 3 2 1

Component Summary measures (calculated from a combination of norm-based scales scores)	Health Domain Scales (raw and norm-based)	Number of items	Items
Physical Health (PCS)	Physical functioning (PF)	10	3a to 3j
	Role-Physical (RP)	4	4a to 4d
	Bodily Pain (BP)	2	7, 8
	General Health (GH)	5	1, 11a to 11d
Mental Health (MCS)	Social Functioning (SF)	2	6, 10
	Mental Health (MH)	5	9b, 9c, 9d, 9f, 9h
	Role-Emotional (RE)	3	5a, 5b, 5c
	Vitality (VT)	4	9a, 9e, 9g, 9i

The derivations of the eight Health Domain Scales Total Scores (Raw and norm-based) and the two component summary measures (calculated from a combination of norm-based scales scores) will be performed using software application delivered by QualityMetric.

Missing data are ignored and the scale is calculated without the missing item. If more than 50 % of the items are missing from any scale, the scale score will not be calculated.

For any given value, if the missing values represent more than 10 % of the population; two analyses will be performed. One analysis using the available values and a second analysis imputing the missing values by the mean value of the available data at the concerned timepoint will be performed.

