1.3.3. Schedule of assessments

Table 1. Schedule of Assessments

Visit	1	2	3	4	5	6	7	8	9	10	11	12	13	14	XX
	Screening	Baseline	3M	6M	9M	12M	15M	18M	21M	24M	27M	30M	33M	36M	Every 3M
Informed Consent	X														
Demographic Data	X														
Medical History	X														
Eligibility Criteria	X	X													
Physical Examination	X	X	X	X	X	X	X	X	X	X	X	X	X	X	X
Vital Signs		X													
ECOG/WHO Performance Status		X			X					X				X	
Randomisation		X													
Testosterone Level [a], [b]		X	X [c]	X [d]	X [d]										
Blood Chemistry and Haematology	X				X										
PSA Level [e]	X		X	X	X	X	X	X	X	X	X	X	X	X	X
Clinical Disease Progression Assessment [f]			X	X	X	X	X	X	X	X	X	X	X	X	X

CCI

CONFIDENTIAL

RAP Final Version 3 [22-JUL-2019]

14/248

Visit	1	2	3	4	5	6	7	8	9	10	11	12	13	14	XX
FACT-P Questionnaire		X			X					X				X	
SF-36 Health Survey		X			X					X				X	
Triptorelin Injection [a]		X	X	X											
Prior and Concomitant Medication/Therapy	X	X	X	X	X	X	X	X	X	X	X	X	X	X	X
Prior and Concomitant Non-Drug Therapy	X	X	X	X	X	X	X	X	X	X	X	X	X	X	X
AEs [1]	X	X	X	X	X	X [1]									
Visit Status	X	X	X	X	X	X	X	X	X	X	X	X	X	X	X

AE, adverse event; CCI, prostate specific antigen; ECOG, Eastern Cooperative Oncology Group; FACT P, functional assessment of cancer therapy prostate; M, month; PSA,

CC1

- a Only for the triptorelin adjuvant treatment group (± 7 days)
- b Always prior to each triptorelin injection (Baseline, 3 months, and 6 months)
- c Evidence of lack of castration at 3 months/Visit 3 will be documented by serum testosterone ≥50 ng/dL (≥0.50 ng/mL) confirmed by a second elevated serum testosterone level at least two weeks later. For the other testosterone assessment time points (Baseline, and 6 and 9 months), no confirmation test is required.
- d If evidence of lack of castration at 3 months/Visit 3, therefore testosterone sampling is not required anymore at Visit 4/Month 6 and Visit 5/Month 9.
- e Starting from Visit 3, any elevated PSA concentration >0.2 ng/mL should be confirmed by a second measurement performed 4 to 6 weeks later. No confirmation test is required after evidence of disease progression (biochemical relapse (BR) and/or clinical disease progression).
- f Clinical disease progression assessments (such as ultrasound [US] guided-biopsy, X-ray, computed tomography [CT] scan, magnetic resonance imaging [MRI]) can be performed at any time during the study at the Investigator's discretion and as per local standard care.

CC1

CONFIDENTIAL

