RAP Final Version 3 [22-JUL-2019]

15/248

CCI

1 Adverse events (AEs) will only be collected until Visit 5/Month 9; this corresponds to three months after the last triptorelin injection for those patients in the triptorelin group. After this visit, only AEs and SAEs related to triptorelin according to Investigator's judgement should be reported (with the exception of AEs resulting in death that should be reported until the end of the study).

Patients will not be withdrawn from the study if study medication is discontinued. Follow-up will continue for all patients every 3 months and for at least 36 months.

1.3.4. *Planned sample size*

It is planned to recruit 226 patients in approximately 10 centres in two countries (China and Russia) according to the Sample Size Determination.

The sample size estimation was based on the primary efficacy endpoint of BRFS. Assuming that with RP alone, the probability of biochemical (PSA) relapse as defined in Section 4.2.1 of the study protocol at 36 months after RP is 40% in high-risk patients (Section 2.1 of the study protocol, Table 1), and anticipating that immediate adjuvant hormonal therapy added to RP will reduce this probability to 20% (percentage considered to be clinically relevant), 113 patients per treatment group (226 in total) are required in order to detect such a difference using a two-sided log-rank test at a significance level of 5% and a power of 90%, assuming a common 1% exponential dropout rate (corresponding to an approximate 5% dropout rate per year).

These 226 patients are required to observe 61 BR in order to achieve 90% power. For patients with no sign of disease progression at 36 months post-randomisation, monitoring will continue until the 61 BR events are observed at the study global level. If the 61 events are observed before all patients complete the 36 months post-randomisation monitoring period, the study will be continued until those patients reach their 36 month visit (Visit 14).

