3.2.1.2. Secondary efficacy analysis

The secondary efficacy analyses will be performed on the ITT population. In these analyses, no interaction will be tested for EFS, OS, disease-specific mortality and PSA doubling time. For serum testosterone, only patients in the triptorelin-treated group will be included in the analysis

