3.2.1.2.6. Serum testosterone

The proportion of castrated (serum testosterone < 50 ng/dL) patients at baseline and 3, 6 and 9 months post-RP will be provided for the triptorelin treatment group. Shift tables between two consecutive visits and between baseline and end of study will be presented of the number and percentage of patients castrated or not.

FACT-P measurements	SF-36v2 measurements

 • Subscales: 
 ○ Physical well-being ○ Social well-being ○ Emotional well-being ○ Functional well-being • Dimensions: 
 ○ General well-being ○ Prostate-specific concerns • Total FACT-P score 	
 • Health Domain Scales: 
 ○ Physical functioning (Raw) ○ Role-Physical (Raw) ○ Bodily Pain (Raw) ○ General Health (Raw) ○ Social Functioning (Raw) ○ Mental Health (Raw) ○ Role-Emotional (Raw) ○ Vitality (Raw) ○ Physical functioning (Norm-based) ○ Role-Physical (Norm-based) ○ Bodily Pain (Norm-based) ○ General Health (Norm-based) ○ Social Functioning (Norm-based) ○ Mental Health (Norm-based) ○ Role-Emotional (Norm-based) ○ Vitality (Norm-based) • Component Summary measures calculated from a combination of norm-based scales scores: 
 ○ Physical Component Summary ○ Mental Component Summary

These HRQoL measurements at baseline and at 9, 24 and 36 months post-RP, will be described using descriptive quantitative statistics for each treatment group (cf. Section 3.2.10 for derived FACT-P and SF-36v2). In addition the change from baseline will also be presented for each of these HRQoL measurements.

For each HRQoL measurement (subscales, dimensions, scales, component summary measures), changes will be analysed using a repeated-measures analysis of covariance using a mixed linear model with patient as a random effect, baseline, group, visit (Month 9, Month 24 and Month 36) and the interaction between group and visit as fixed effects. Correlation structures (auto-regressive (AR(1)), compound symmetry (CS) and unstructured (UN)) will be tested and the best one will be considered for the model (the model with the smaller AIC will be chosen):

Change = baseline + group + visit + group*visit + e

With:

- baseline, group, visit and group*visit as fixed effects,
- e: error $\sim N(0, \sigma e^2)$.

The syntax with SAS using the MIXED procedure will be:

```
CCI [REDACTED]
```

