Laboratory data (haematology, biochemistry) will be listed in SI units and abnormal values will be flagged (High [H], Low [L], clinically significant [C], NCI-CTC grade (G)) where applicable. Any unscheduled laboratory assessments will be flagged [U] in the listings.

For haematology and biochemistry parameters the baseline will be defined as the screening values.

Summary statistics (mean, median, SD and range as appropriate) by treatment group and overall will be presented for clinical laboratory tests at each assessment (screening and 9 month) with change from baseline.

Shift tables will be presented of the number and percentage of patients with below, within or above normal range. For laboratory data, abnormal values will be flagged in the data listings and a list of clinically significant abnormal values will be presented.

In case of available retest sample, values of retest sample will be used instead of the first sample, except at baseline where the last test available before first injection of treatment will be used.

3.2.2.3. *Vital signs*

Descriptive summary statistics will be provided on safety population according to the actual treatment approach followed for vital signs. It includes assessments as detailed in the Section 1.3.2.3 'Vital signs'.

3.2.3. *Missing data and outliers*

3.2.3.1. *Missing data*

Missing data will not be imputed and dropouts will not be replaced.

Rules for missing data imputation for HRQoL will be addressed in 3.2.10 Derived Data.

3.2.3.2. *Missing or incomplete dates*

In all listings, missing or incomplete dates should be left as they have been recorded. However, for calculation / sorting / assignation based on dates, the following methods will be used:

- The most conservative approach will be systematically considered (i.e. if the onset date concomitant medication is missing / incomplete, it is assumed to have occurred during the study treatment phase except if the partial onset date or other data [stop date, ...] indicates differently).
- A missing/incomplete date of medical history or disease diagnosis will be assumed to have occurred before the study inclusion.
- If a partial date and the associated information do not allow to state about the assignation to a group / category, all the possible groups / categories will be considered (i.e.: a medication with partial start and stop dates could be considered as prior and concomitant treatment).

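### Month 6 and Month 9 castration rates largely leave out the confirmed Month 3 failures, so they overstate the triptorelin-group rate unless those failures later castrate at least as often as the sampled patients

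*SAP*

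**What the plan says.** Section 3.2.1.2.6 defines the measure: "The proportion of castrated (serum testosterone < 50 ng/dL) patients at baseline and 3, 6 and 9 months post-RP will be provided" for the triptorelin group. It adds: "Shift tables between two consecutive visits and between baseline and end of study will be presented". Section 3.2.1.2 puts the secondary efficacy analyses on the ITT population and restricts this one by arm: "For serum testosterone, only patients in the triptorelin-treated group will be included in the analysis".

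The schedule in section 1.3.3 treats some of these patients differently. Under footnote c, lack of castration at Month 3 means testosterone of at least 50 ng/dL, confirmed by a second elevated value. For such a patient, footnote d says: "therefore testosterone sampling is not required anymore at Visit 4/Month 6 and Visit 5/Month 9". The closing note of the same section keeps them under observation: "Follow-up will continue for all patients every 3 months and for at least 36 months".

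The rules for missing values are general. Section 3.2.3.1 states: "Missing data will not be imputed and dropouts will not be replaced". The only exception it names is for quality of life: "Rules for missing data imputation for HRQoL will be addressed in 3.2.10 Derived Data". Section 3.1.5 shows the number of missing values but leaves them out of percentages, and section 3.2.13 uses non-missing observations as the denominator. Section 3.2.10 classes a patient from measured values alone: "Not castrated if the testosterone level is superior or equal to 50 ng/dL for the test and confirmation test". No rule in the text shown gives an unsampled Month 3 failure a status at Month 6 or 9.

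**The concern.** The missing values here are created by the plan and triggered by the outcome being reported: the patients released from sampling are the ones who have just failed the criterion. They remain randomised, in the ITT population and in follow-up, so they belong to the group the rate claims to describe. The Month 6 and 9 percentages instead mainly describe patients without a confirmed failure at Month 3, and section 3.2.1.2.6 does not say so.

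A reader would take these figures as whole-group castration rates. The rate could also appear to rise from Month 3 to Month 6 merely because failures left the denominator. The later shift tables lose the same patients from their castrated and not-castrated cells, so they largely cannot show whether a failure persisted. In addition, the text shown does not say which visit is the end of study for testosterone, whose last scheduled sample is Month 9.

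**Working it through.** The SAP states no castration rate and no expected Month 3 failure rate, so there is no figure to reproduce. The check is algebra plus an illustration.

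**Inputs**
- Triptorelin group: 113 patients (sections 1.2.1 and 1.3.4).
- *f*: confirmed Month 3 failures in follow-up without a sample at the visit. Not given; assumed 2, 6 or 11.
- *N*: sampled patients plus *f*. Taken as 113.
- *c*: castrated share of the sampled patients. Not given; assumed 100%, with 104/107 as a variant.
- *l*: share of the *f* patients truly castrated at the visit. Not given; varied from 0 to *c* and above.

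**Formula**
- Reported rate = *c*, because unsampled patients are outside the denominator.
- Whole-group rate = [(*N* − *f*)*c* + *f l*]/*N*.
- Overstatement = reported minus whole-group = (*f*/*N*)(*c* − *l*).

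This is positive when *l* < *c*, zero when *l* = *c* and negative when *l* > *c*.

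**Numbers, with *N* = 113 and *c* = 100%**

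| *f* | *l* = 0 | *l* = 50% | *l* = *c* |
|---|---|---|---|
| 2 | 2/113 = 1.8 points | 0.9 | 0 |
| 6 | 6/113 = 5.3 points | 2.7 | 0 |
| 11 | 11/113 = 9.7 points | 4.9 | 0 |

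**Variant with some failures among the sampled.** With *f* = 6, *c* = 104/107 and *l* = 0, the reported rate is 104/107 = 97.2%. The whole-group rate is 104/113 = 92.0%. The gap is 5.2 points.

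**Opposite direction.** With *c* = 98% and every failure castrating later (*l* = 100%), even 17 failures give (17/113)(0.98 − 1.00) = −0.3 points. When the sampled rate is high, the error can be large only upward.

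**Does the proposed second rate treat withdrawals evenly?** Take *f* = 6, *c* = 100%, *l* = 0, and the same withdrawal share *w* among the 107 others and the 6 failures.
- Counting only failures still in follow-up: 107(1 − *w*)/[107(1 − *w*) + 6(1 − *w*)] = 107/113 = 94.7% for every *w*.
- Keeping withdrawn failures in the denominator: 107(1 − *w*)/[107(1 − *w*) + 6]. This is 94.6% at *w* = 2.5% (six months at the approximate 5% per year of section 1.3.4) and 94.1% at an assumed *w* = 10%.

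Limiting the count to failures still in follow-up therefore avoids a new, if small, distortion.

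**The case against.** The best case against runs as follows.

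- **Disclosure.** Section 3.1.5 requires the number of missing values in the tables, and sections 3.2.13 and 7 allow footnotes that specify a denominator. With the Month 3 rate alongside, much of the conditioning could be visible. This stands in part. The footnote is only for use where judged necessary, a missing count does not separate a known failure from a skipped visit, and the percentage stays uncorrected.
- **Unseen text.** The table shells are not in the copy at hand, and the text near this section looks incomplete. This stands as a limit on what can be said about layout, carry-forward and the end-of-study visit. The denominator and missing-data rules that are visible all point one way.
- **Unknown size.** The number of failures could be zero or negligible. A failure needs two elevated values, sampling is not required rather than forbidden, and a late confirmation sample could fall in the Month 6 window. All of this stands, and is why the claim is that failures are largely, not wholly, omitted.
- **Unknown direction.** Failures might castrate later, and the text shown does not settle how they are managed after Month 3. This also stands, and is why the bias is stated conditionally.
- **The remedy has its own bias.** Counting an unmeasured patient as not castrated is a worst-case assignment and understates the rate if any of them later castrate. True, and this is the reason to show it beside the observed rate and not in its place.

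**Conclusion.** The concern holds. Followed as written, the plan gives Month 6 and 9 rates that are mainly conditional on no confirmed failure at Month 3 but are presented as rates for the triptorelin group. The direction is upward on the condition that omitted failures castrate later less often than sampled patients. The amount depends on a failure count the document does not supply, so the tabulated gaps illustrate it and are not estimates. The consequence is limited: no test or between-arm comparison rests on this endpoint. The change should still be made, because the affected figures are the plan's own measure of whether castration was maintained after Month 3, and the correction is cheap.

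**What to change.** In section 3.2.1.2.6, with a matching exception in section 3.2.3.1, report two labelled rates side by side at Months 6 and 9:

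- **(a) Observed-sample rate**, labelled as mainly conditional on no confirmed failure at Month 3.
- **(b) Rate counting known failures.** Confirmed Month 3 failures still in follow-up at the visit without a sample count as not castrated; the denominator is sampled patients plus those failures. Still in follow-up can mean a visit attended in the analysis window of section 3.2.11 (days 139 to 229 for Month 6, days 230 to 321 for Month 9), so withdrawn failures and withdrawn responders both drop out.

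For example, suppose there are 6 failures, none of them sampled again, and all other sampled patients are castrated. If 3 of the 107 others and 1 failure withdraw, (a) is 104/104 = 100% and (b) is 104/109 = 95.4%.

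Show these failures as their own row in the shift tables, and state which visit is the end of study for testosterone.

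The cost is two sentences in 3.2.1.2.6, one exception in 3.2.3.1, one extra row per table, and a derived flag linking confirmed Month 3 status, attendance and absence of a sample. No sampling changes. The downside is that (b) is slightly less favourable and misclassifies any unsampled late castrator; (a) beside it leaves the observed data unchanged.
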